In comparison to morphine sulfate IR, higher PID scores and a greater proportion of patients achieving >33% or >2 point pain intensity score reduction have been reported with Lazanda[®].^{14,15} In one study, pain intensity difference at 15 minutes (mean \pm SD) was 3.0 ± 0.2 and 2.7 ± 0.2 (p<0.05) for Lazanda and morphine sulfate IR, respectively.¹⁵ Decreases in pain intensity by 2 or more was seen in 52.4% and 45.4% of patients (p<0.05) 10 minutes after Lazanda and morphine sulfate IR administration.¹⁴ In another study, PI scores after 5 minutes

(5.6 vs. 5.8) and after 20 minutes (3 vs 3.4) were significantly lower for Lazanda versus intranasal fentanyl. Five minutes after administration, more patients experienced a >33% pain intensity reduction (~13% vs. <5%; $p < 0.05$), while at 20 minutes after administration, more patients experiences a >50% pain intensity reduction (~71% vs. ~55%; $p < 0.05$) with Lazanda.¹⁶

Common adverse events are drowsiness, nausea, vomiting, and constipation, with most these symptoms mild to moderate in severity. Nasal symptoms, including obstruction, discomfort, itching, sneezing, dryness, and crusting have also been mostly reported as mild and moderate in severity.¹²⁻¹⁷ Ninety-nine serious adverse events have been reported in 3 studies, with 25 of these deemed related to fentanyl pectin nasal spray.^{12,15,17} Two deaths possibly related to fentanyl pectin nasal spray have been reported.^{15,17} In one death, the patient developed cyanosis, loss of consciousness, and upper airway obstruction after an apparent unintentional overdose during a breakthrough pain episode.¹⁷

The initial starting dose for this study will be Lazanda 100 mcg prior to radiation therapy simulation. A 100 mcg dose is the initial dose of Lazanda for all patients as detailed in the product package insert. Lazanda dose titration will follow the guidelines as indicated in the product package insert from the baseline visit through the end of radiation therapy. If the subject does not experience relief after 30 minutes, he or she may take another 100 mcg but must wait at least 2 hours from the first spray before administering this second 100 mcg dose.

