4.2.1 Radiation Simulation Visit(s)

To determine an individual patient's effective and tolerable Lazanda dose, each subject will undergo dose titration during the radiation simulation visit. Lazanda dose for all subjects on study, including those switching from another fentanyl product, will be determined according to the following procedures:

- 15 minutes prior (T-15) to beginning the radiation therapy simulation, subjects will receive an initial dose of 100 mcg (1 spray) of Lazanda in one nostril prior to lying on the CT simulation hard surface.
- If adequate analgesia is obtained within 30 minutes of administration of the 100-mcg single spray, subsequent pain episodes will be treated with this dose.
- If the subject does not experience relief after 30 minutes, he or she may take another 100 mcg in the opposite nostril **but must wait at least 2 hours** (i.e., T-15 + 2 hours) from the first spray before administering this second 100 mcg dose. The subject may delay or reschedule the simulation (within a 14 days period) or radiation delivery to achieve the adequate pain control dose.
- If adequate analgesia is still not achieved, the subject will continue to dose escalate in a step-wise manner at a minimum of 2 hours between each subsequent escalation until adequate analgesia with tolerable side effects is achieved. A maximum of 4 doses or 400 mcg allowed per day.
- Dose titration steps are further detailed in **Table 1**.

Table 1: Lazanda Dose Titration Steps

Lazanda Dose	Using
100 mcg	1 x 100 mcg spray
200 mcg	2 x 100 mcg spray (1 in each nostril)
400 mcg	4 x 100 mcg spray (2 in each nostril, alternate nostrils) or 1 x 400 mcg spray

Each bottle contains a total of 8 sprays. Lazanda bottles come in 100 mcg or 400 mcg dose. If using dose of 100 mcg with the 100-mcg spray, the patient would have total of 8 doses in a single bottle. If using dose of 200 mcg with the 100-mcg spray, the patient would have total of 4 doses in a single bottle. If using dose of 400 mcg with the 100-mcg spray, the patient would have total of 2 doses in a single bottle. Alternately, if using a bottle of the 400-mcg spray at a dose of 400 mcg, the patient would have total of 8 doses in a single bottle.

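### For subjects not relieved by the first 100 mcg, the titration text and the titration table give different second steps, so the dose carried to the radiation fractions can be read as 100 or 200 mcg

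*Combined protocol and SAP*

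**What the plan says.** Every subject starts at 100 mcg. If that gives adequate analgesia within 30 minutes, section 4.2.1 is clear: "subsequent pain episodes will be treated with this dose".

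If it does not, the sources are as follows.

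- **Text.** Section 4.2.1: "he or she may take another 100 mcg in the opposite nostril". Section 1.2 describes the same step and sets the interval: the subject "must wait at least 2 hours from the first spray before administering this second 100 mcg dose". If analgesia is still inadequate, "the subject will continue to dose escalate in a step-wise manner"; the bullet does not state the next level and the list then points to Table 1.
- **Table 1 of section 4.2.1** (the titration table, not the assessment table in section 4.1 that carries the same number). The levels are 100, 200 and 400 mcg. The 200 mcg level is "2 x 100 mcg spray (1 in each nostril".
- **Text below that table.** "If using dose of 200 mcg with the 100-mcg spray, the patient would have total of 4 doses in a single bottle".
- **Section 8.1 and Appendix H.** Both describe 200 mcg as one spray in each nostril.
- **Appendix I log.** It has one simulation row each for 100, 200 and 400 mcg, and an instruction to mark a row not applicable when no higher dose is needed.
- **Schedule of Events, footnote 7.** A second dose follows 2 hours later according to the label. Its size is not given.

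Section 4.2.1 then makes the minimal effective dose from simulation the pre-medication for up to 10 fractions. Section 4.2.2 says that this dose is the one described by both the section 4.2.1 scheme and Table 1.

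**The concern.** The text repeats the same dose at the second step, while the table and the log move to the next level. A coordinator titrating from the bullets and one titrating from Table 1 or the log would give a different second administration. Even where the same 100 mcg is repeated and works, nothing says which dose has been shown to be effective: the 100 mcg just given, or the 200 mcg level that the log places second.

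The result is carried forward. It sets the dose of a Schedule II opioid that the subject self-administers before each fraction, and under section 8.1 it also guides the further supply. Section 4.2.1 lets the investigator adjust the dose if the response changes markedly, but that does not define the dose first carried. What is at stake is whether similar subjects are dosed alike, and safely.

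**Working it through.** **1. Is 200 mcg one dose in the table?** Table 1 does not use the word single, so this has to be inferred. The plan's own bottle count answers it. With 8 sprays per bottle and the 100-mcg spray:

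- 100 mcg: 8 / 1 spray = 8 doses
- 200 mcg: 8 / 2 sprays = 4 doses
- 400 mcg: 8 / 4 sprays = 2 doses

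These reproduce the stated 8, 4 and 2. The 200 mcg level is therefore a two-spray dose, in line with section 8.1, Appendix H and the separate log row with its own three pain-score columns.

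**2. The second administration under each source.**

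- Text (sections 1.2 and 4.2.1): 100 mcg, cumulative 100 + 100 = 200 mcg over at least 2 hours.
- Table 1 and Appendix I, if the levels are taken in order: 200 mcg, cumulative 100 + 200 = 300 mcg.
- Footnote 7: size not stated, so it does not decide between them.

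**3. Ways to fit text and table together.**

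- *Competing ladders.* The text says 100 then 100; the table says 100 then 200.
- *Optional repeat, then escalation.* The text says the subject may repeat 100 mcg; escalation through Table 1 follows. The ladder is 100, optional 100, 200, 400.
- *Two separated sprays as the 200 mcg level.* The second spray goes in the other nostril and the next bullet speaks of continuing to escalate, so the two sprays together could be the one-per-nostril level.

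Each reading is open on the wording, and no section chooses among them.

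**4. Dose carried after relief on the second 100 mcg.**

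- Taken as the dose just given: 100 mcg.
- Taken as the second Table 1 level, or as the cumulative amount: 200 mcg.
- Ratio: 200 / 100 = 2.
- Over the maximum of 10 fractions: 10 x 100 = 1,000 mcg or 10 x 200 = 2,000 mcg.

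The third reading in step 3 points to 200 mcg. It does not settle the matter, because the titration bullet calls the later spray a 100 mcg dose in its own right, while the fraction dose is given once, 15 minutes before lying down.

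**5. How many subjects.** The documents give no rate of relief at the first 100 mcg in this setting. The range is 0 to all of the approximately 6 subjects in the Study Summary and section 9.2. (Section 4.1 and the accrual table still show 15.) The carried dose is unclear mainly for those relieved at the second step.

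**6. Records.** Sections 4.2.2 and 5.1.11.6 and Appendix H capture each administered dose. The only gap is in Appendix I, where a repeated 100 mcg has no row for its pain scores.

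**The case against.** The strongest reply is that the protocol names a governing source. The Study Schema and sections 1.2 and 4.1 say that titration follows the package insert, and footnote 7 and Appendix I refer to the label. Staff who follow that document may meet only one ladder in practice. It is not among the documents reviewed, so this cannot be checked. It limits what can be said about practice, but section 4.2.1 also writes out its own procedure, and a reference elsewhere does not make the protocol's text, table and log agree.

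A second reply is that Table 1 lists dose levels and how to deliver them, and does not label 200 mcg as the second administration. Read with the permissive wording of the bullet, text and table could be complementary. That is fair, and it is one of the three readings above, but it still leaves the carried dose undefined.

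A third reply is that the practical effect is bounded. Both 100 and 200 mcg are listed levels, dosing is watched by clinic staff, the investigator may adjust, and the trial is a small case series. All of this stands, and it is why the point is confined to dosing consistency and safety.

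A reader might infer two stronger things, and the documents support neither.

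- *That section 4.2.1 counts doses in two ways.* Two 100-mcg sprays hours apart are two doses; two sprays given together as 200 mcg are one. These are different administrations, so there is no contradiction in the counting.
- *That titration breaks the daily limit.* The limit is "A maximum of 4 doses or 400 mcg allowed per day", and 100 + 200 + 400 = 700 mcg. But the limit can be read as a cap at whichever figure is reached first, in which case that course is barred on one day. The steps may also be spread out: "The subject may delay or reschedule the simulation (within a 14 days period". The protocol does not direct a subject to take every level on one day. What remains is that it does not say how the two halves of the limit are to be read alongside Table 1.

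**Conclusion.** The point holds for subjects not relieved by the first 100 mcg. The protocol's own passages differ on the second titration step, and after relief on a second 100 mcg the fraction dose can be read as 100 or 200 mcg. The difference is two-fold per fraction; the 1,000 against 2,000 mcg total assumes all 10 fractions and no later adjustment. The number of subjects affected cannot be estimated from the documents. The wording difference is certain. How far it would reach practice is less so, because the package insert may guide staff. Subjects relieved by the first spray are not affected, and the reported dose data are not lost. Because it concerns the repeated dose of a self-administered opioid, it should be corrected even though few subjects may be involved.

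**What to change.** The sponsor and investigator should reconcile section 1.2, section 4.2.1 (bullets, Table 1 and the carried-dose paragraph), section 4.2.2, footnote 7 of the Schedule of Events and Appendix I, so that they:

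- describe one titration ladder, including whether a repeated 100 mcg is a step in it;
- define the dose carried to the fractions after relief at the second step;
- have Appendix I rows that match that ladder;
- state how the daily limit of 4 doses or 400 mcg is to be read alongside Table 1.

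Which dose or limit applies is for the clinical team. The cost is a wording amendment to the protocol and a revised Appendix I form; no design, sample size or analysis changes.

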	
pain therapies (i.e., glucocorticoids, NSAIDs, anticonvulsants, pharmaceutical cannabinoids, tricyclic antidepressants).
 
 4. Patient is ≥ 18 years of age. 5. ECOG Performance Status ≤ 3 6. Negative pregnancy test prior to initiating study treatment for females of childbearing potential. 
Key Exclusion Criteria
 
 1. Patient is currently receiving or has received another investigational agent within 30 days or monoamine oxidase inhibitor within 14 days prior to study drug administration. 2. Patients who require immobilization with a thermoplastic mask for radiation treatment. 3. Patient is planned to receive interventional procedures (i.e., surgery) that may affect study outcomes. 4. Patient has a history of hypersensitivity to fentanyl or opioids. 5. Patient is pregnant or nursing. 6. Patient is being treated with oxymetazoline for allergic rhinitis or has a disorder or current medication use likely to adversely affect normal functioning of the nasal mucosa. 7. Patient has uncontrolled or rapidly escalating background pain. 8. Patient has bradyarrhythmia. 9. Patient is medically unstable. 10. Patient is thought to be at risk for misuse, abuse, addiction or overdose for Schedule II controlled substance, as evidenced by an Opioid Risk Tool (ORT)² score ≥ 8 and review of the California Prescription Control Monitoring Program (PDMP) Controlled Substance Utilization Review and Evaluation System (CURES) report demonstrates multiple prescribing providers and/or multiple pharmacies in the last 30 days.

Study Product(s), Dose, Route, Regimen
	
Lazanda (fentanyl) nasal spray is supplied as a 5-mL bottle containing 8 sprays of 100 mcL of solution containing either 100 mcg or 400 mcg fentanyl base. Lazanda will be self-administered intranasally by subjects participating in this study. Subjects will undergo dose titration with Lazanda to determine the minimum effective and tolerable dose during their radiation simulation visit. This dose will be used as pre-medication prior to any further radiation therapy.

Duration of administration
	
Subjects will receive Lazanda at their radiation simulation visit and again as pre-medication prior to each radiation treatment (fraction), for an estimated treatment period of 10 days based on the patient's radiation treatment plan.

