Lazanda titration should be done with caution in patients with chronic obstructive pulmonary disease or preexisting medical conditions predisposing them to respiratory depression and in patients susceptible to intracranial effects of CO₂ retention. Caution should also be used in patients on central nervous system (CNS) depressants and potent CYP3A4 inhibitors.

The minimal effective intranasal dose from the radiation therapy simulation will be the dose used as pre-medication prior to any further radiation therapy fractions (up to 10 fractions). Lazanda should be administered 15 (T-15) minutes prior to laying on the hard surface for each simulation visit. If the response to the titrated Lazanda dose markedly changes, an adjustment of dose may be necessary to ensure that an appropriate dose is maintained as deemed by the investigator.

Subjects will be instructed on the proper use of Lazanda as follows:

- 1) Prime the device before use by spraying into the pouch (4 sprays in total). If study drug has not been used for 5 days, re-prime by spraying once.
- 2) Insert the nozzle of the Lazanda bottle a short distance (about ½ inch) into the nose and point towards the bridge of the nose, tilting the bottle slightly.
- 3) Press down firmly on the finger grips until hearing a “click” and the number in the counting window advances by one.

Subjects will also be advised that the fine mist spray is not always felt on the nasal mucous membrane and to rely on the audible click and advancement of the dose counter to confirm a spray have been administered.

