Appendix I. NRS Scale Log

		NRS Score Log		
		Protocol Number	Participant No.	Participant Initials
		HRPP#XXXXXX		
Instructions for completion:				

 • Use the NRS score scale, where 0 is no pain, 5 is moderate pain and 10 is worst pain • If the 100 mcg dose not achieve adequate pain control at the first assessment of the simulation visit, the subject will receive a second dose 2 hours later as per label until the optimal dose is obtained. If not practical the subject will delay or reschedule the next assessment of the simulation (within a 14 days period) or XRT delivery. Mark N/A if a higher dose is not required. • Palliative radiation treatments usually last 15 minutes or less, are completed once a day, five days a week, up to 10 days in duration. Mark N/A if fraction 6 to 10 are not required. 				
Visit/Event		T (-)15: 15 minutes prior to laying down on traetment surface	T0 Laying down on treatment surface	T+15: 15 minutes after laying down on the treatment surface
Mock/ Baseline Visit				
Radiation Therapy Simulation	Lazanda 100mcg			
	Lazanda 200mcg			
	Lazanda 400mcg			
Radiation Therapy	Fraction 1			
	Fraction 2			
	Fraction 3			
	Fraction 4			
	Fraction 5			
	Fraction 6			
	Fraction 7			
	Fraction 8			
	Fraction 9			
	Fraction 10

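### The daily limit in Section 4.2.1 (4 doses or 400 mcg) does not agree with the plan's own 100-200-400 mcg titration levels, and nothing says which part governs

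*Combined protocol and SAP*

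**What the plan says.** Section 4.2.1 starts titration at one level for everyone: "subjects will receive an initial dose of 100 mcg (1 spray) of Lazanda in one nostril". If relief is not obtained, "he or she may take another 100 mcg in the opposite nostril", at least 2 hours after the first spray. If analgesia is still inadequate, the subject is to "continue to dose escalate in a step-wise manner at a minimum of 2 hours between each subsequent escalation until adequate analgesia with tolerable side effects". The limit follows at once: "A maximum of 4 doses or 400 mcg allowed per day".

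The titration table in that section (Lazanda Dose Titration Steps) gives three doses: 100 mcg as one spray, 200 mcg as one 100-mcg spray in each nostril, and 400 mcg as four 100-mcg sprays or one 400-mcg spray. The Appendix I log has a simulation row for each, the last being "Lazanda 400mcg".

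On timing, the Study Summary says subjects are titrated to "determine the minimum effective and tolerable dose during their radiation simulation visit", and the opening sentence of 4.2.1 also speaks of one visit. But the heading of 4.2.1 allows for several visits, and 4.2.1, footnote 7 of the Schedule of Events and Appendix I all allow rescheduling within 14 days.

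The result is carried forward: "The minimal effective intranasal dose from the radiation therapy simulation will be the dose used as pre-medication", for up to 10 fractions.

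**The concern.** A daily opioid limit should give the same answer to everyone who applies it, and this one does not. A coordinator who reads 400 mcg as a daily total stops a subject who is still in pain after 100 and 200 mcg. One who counts doses gives the 400-mcg step. The limit is also one of the few numerical safeguards in the plan: Section 4.2.2 requires no additional monitoring of vital signs after dosing, and Appendix B allows strong CYP3A4 inhibitors.

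The statistical stake is what the carried-forward dose means. If titration ends because the limit was reached, the dose used at the fractions has not been shown to be effective, yet the plan has no other label for it. The models in Sections 9.3.1 and 9.3.4 contain no term for Lazanda dose. The Appendix I log tells staff only to mark a row as not applicable when a higher dose is not needed, and has no entry for toxicity or for the limit. A reader of the results could not tell a subject titrated to effect from one stopped by the limit.

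**Working it through.** The plan does not derive its limit, so there is no calculation to reproduce. The check is whether the limit fits the titration levels.

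**Inputs**, all from Section 4.2.1: levels of 100, 200 and 400 mcg; a second step worded as a further 100 mcg; at least 2 hours between steps; a limit of 4 doses or 400 mcg per day.

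**Do the two parts agree?** Total at the dose limit = 4 × level.

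- 100 mcg: 4 × 100 = 400 mcg. They agree.
- 200 mcg: 4 × 200 = 800 mcg. They differ 2-fold.
- 400 mcg: 4 × 400 = 1,600 mcg. They differ 4-fold.

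Since the smallest dose is 100 mcg, a daily total of 400 mcg can never contain more than 400 / 100 = 4 doses. So if 400 mcg is cumulative and both parts must hold, the dose count adds nothing. That does not show which reading was meant, only that the sentence does not settle it.

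**Can the ladder be completed in one day?** Shortest time = (doses − 1) × 2 h.

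| Sequence on one day (mcg) | Running total (mcg) | Doses | Shortest time | 400 mcg as daily total | 4 doses |
|---|---|---|---|---|---|
| Full doses: 100, 200, 400 | 100, 300, 700 | 3 | 4 h | exceeded by 300 | met |
| 100, a further 100, then 200, 400 | 100, 200, 400, 800 | 4 | 6 h | exceeded by 400 | met |
| 100, a further 100, then 400 | 100, 200, 600 | 3 | 4 h | exceeded by 200 | met |
| Added increments: 100, +100, +200 | 100, 200, 400 | 3 | 4 h | met | met |

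For the full-dose ladder, 700 / 400 = 1.75. If 400 mcg is instead a ceiling on each single dose, all four sequences meet it.

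The fourth sequence meets both parts under any reading, but its 400 mcg is a sum built up over at least 4 hours. The titration table defines 400 mcg as one dose, so that sequence does not test the dose that would be given before a fraction.

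**Over more than one day.** With 400 mcg as a daily total, the full-dose ladder fits in two days: 100 + 200 = 300 mcg on one, and a single 400 mcg on another.

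**The case against.** The strongest reply is that the plan does not confine titration to one day. The rescheduling provision sits in the same list of steps as the limit and is repeated in footnote 7 and Appendix I. Section 4.2.1 also refers to each simulation visit, as though there may be several. That stands: a reader might infer that the 400-mcg level can never be tested, and the documents do not support this. What remains is that rescheduling is optional in 4.2.1, is offered where a same-day repeat is impractical in footnote 7 and Appendix I, and is nowhere tied to reaching the limit. It gives a way round the limit without saying what the limit means.

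Second, a two-part maximum is ordinarily read as whichever is reached first, and titration is tied to the package insert, which is not among these documents. So 1,600 mcg should be taken as the arithmetic of one part alone, not as a total the plan intends. This is fair, but the protocol does not state the ordinary reading, and under it the full-dose ladder still fails on one day.

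Third, the 700 mcg depends on full doses, and added increments give exactly 400 mcg. That is correct. It shows that the second-step wording has to be settled together with the limit.

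Fourth, no passage tells staff to carry forward a dose that failed, and later adjustment is allowed. This also stands in part: a limit-stopped dose is a possibility, not an instruction. But the adjustment clause covers a response that markedly changes, which does not clearly include one that was never adequate.

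**Conclusion.** The point holds as an internal contradiction. The limit in Section 4.2.1 cannot be applied consistently alongside the titration table and Appendix I. Its parts agree only at 100 mcg. Read as a cumulative total, 400 mcg excludes same-day completion of the full-dose ladder (700 mcg), while the dose count allows it. This rests on taking the table levels as single doses, as the table defines them.

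Two stronger conclusions do not follow. The 400-mcg level is not out of reach, since it can be given on another day. Nor can it be said that one or two affected subjects would change the conclusion. The documents do not say how many subjects would need more than 200 mcg, set no success threshold, and plan to report by participant. One subject is 1/6 = 17% to 1/5 = 20% of the sample in Section 9.2 (1/15 = 7% of the 15 in Section 4.1), so an effect is possible but cannot be sized. The sample size and error rates are not touched. No view is taken on which limit is right.

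**What to change.** The investigators should reconcile four places: the limit in 4.2.1; the second step (a further 100 mcg in the text, including Section 1.2, against 200 mcg in the titration table and Appendix I); the single titration visit in the Study Summary and the opening of 4.2.1; and the simulation rows of Appendix I. The text should state whether 400 mcg applies per dose or cumulatively, whether both parts must hold, and, if the limit is cumulative, how titration continues after it is reached.

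Three changes to records and reporting go with this:

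- Add a field to the Appendix I log for why titration stopped: adequate analgesia, toxicity or daily limit.
- Make the Appendix H form capture the total daily dose. Sections 4.2.2 and 5.1.11.6 already require it, but the form has only date, time and dose.
- Do not report a dose at which titration was stopped by the limit as a minimal effective dose.

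The cost is protocol wording, one or two form fields and possibly a second titration day for some subjects, which 4.2.1 already allows.
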